4.3 Exploratory Objectives

- (1) To characterize the T-cell inflamed phenotype in mesothelioma patients via presence of CD8 tumor infiltrating lymphocytes (TILs) and/or use of a gene expression signature (Nanostring).*
- (2) To evaluate other immune escape mechanisms including IDO expression, Tregs (FOXP3 expression), MDSCs and other checkpoints by immunohistochemistry (or other methods e.g. Flow Cytometry (also see 4)).*
- (3) To determine PD-L1 expression by mass spectrometry and correlate with tumor response, PD-L1 expression by IHC, and the T-cell inflamed phenotype.*
- (4) To determine the immune cell populations present in fresh tumor (when available), via tumor digests and mass spectrometry-based flow cytometric analysis (e.g. using CyTOF) in a multiplex fashion in patients with fresh tumor tissue.*
- (5) To characterize the T-cell receptor repertoire of TILs compared to circulating T-cells in mesothelioma patients with available fresh frozen tissue (spectrotyping, T-cell repertoire sequencing (e.g. using the Adaptive platform))*
- (6) To develop a radiomics-based method to quantify acute immunotherapy-induced pneumonitis and automatically identify patients with pneumonitis based on quantifiable changes in a patient's CT scans.

* As available fresh biopsy tissues (or alternatively/concurrently circulating T-cells) will be assessed for baseline status or treatment effects.

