6.1.3 Subject Exclusion Criteria

The subject must be excluded from participating in the trial if the subject:

1. Is currently participating in or has participated in a study of an investigational agent or using an investigational device within 2 weeks (4 weeks for monoclonal antibodies) of the first dose of treatment

2. Side effects from prior treatment have not resolved to \leq grade 1 (or baseline due to previously administered agent/pre-existing conditions).
3. Has a diagnosis of immunodeficiency or is receiving systemic steroid therapy or any other form of immunosuppressive therapy within 7 days prior to the first dose of trial treatment.
4. Has had a prior monoclonal antibody within 4 weeks prior to study Day 1 or who has not recovered (i.e., \leq Grade 1 or at baseline) from adverse events due to agents administered more than 4 weeks earlier.
5. Has had prior chemotherapy, targeted small molecule therapy, or radiation therapy within 2 weeks prior to study Day 1 or who has not recovered (i.e., \leq Grade 1 or at baseline) from adverse events due to a previously administered agent.
 - Note: Subjects with \leq Grade 2 neuropathy are an exception to this criterion and may qualify for the study.
 - Note: If subject received major surgery, they must have recovered adequately from the toxicity and/or complications from the intervention prior to starting therapy.
6. Has a known additional malignancy that is progressing or requires active treatment. Exceptions include basal cell carcinoma of the skin, squamous cell carcinoma of the skin, in situ cervical cancer, or other indolent cancers which either have undergone curative-intent therapy or inactive (i.e. not expected to limit life expectancy or interfere with therapy).
7. Has known active central nervous system (CNS) metastases and/or carcinomatous meningitis. Subjects with previously treated brain metastases may participate provided they are stable (without evidence of progression by imaging for at least four weeks prior to the first dose of trial treatment and any neurologic symptoms have returned to baseline), have no evidence of new or enlarging brain metastases, and are not using steroids for at least 7 days prior to trial treatment.

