6.7.2 Prohibited Concomitant Medications

Subjects are prohibited from receiving the following therapies during the Screening and Treatment Phase (including retreatment for post-complete response relapse) of this trial:

- Anti-cancer systemic chemotherapy or biological therapy
- Immunotherapy not specified in this protocol
- Chemotherapy not specified in this protocol
- Investigational agents other than pembrolizumab

- Radiation therapy
 - Note: Radiation therapy to a symptomatic solitary lesion or to the brain may be allowed after consultation with the PI.
- Live vaccines within 30 days prior to the first dose of trial treatment and while participating in the trial. Examples of live vaccines include, but are not limited to, the following: measles, mumps, rubella, chicken pox, yellow fever, rabies, BCG, and typhoid (oral) vaccine. Seasonal influenza vaccines for injection are generally killed virus vaccines and are allowed; however intranasal influenza vaccines (e.g. Flu-Mist®) are live attenuated vaccines, and are not allowed.
- Glucocorticoids for any purpose other than to modulate symptoms from an event of clinical interest of suspected immunologic etiology. The use of physiologic doses of corticosteroids may be approved after consultation with the Drug Manufacturer.

Subjects who, in the assessment by the investigator, require the use of any of the aforementioned treatments for clinical management should be removed from the trial. Subjects may receive other medications that the investigator deems to be medically necessary.

The Exclusion Criteria describes other medications which are prohibited in this trial.

There are no prohibited therapies during the Post-Treatment Follow-up Phase.

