6.13.8 Flow Cytometric Analysis of PBMCs

Blood samples will be obtained at baseline and after cycle 3 using 2 (two) lavender- (EDTA) (or alternatively green- (sodium heparin)) tubes. Processing will occur in the HIM core facility following standard protocol for processing and storage of cell suspensions for later analysis by flow cytometry. Subsequent FACS/CyTOF multiplex immune marker analysis will be performed. Markers include those listed above as well as additional immune markers and are subject to change.

Section 6.13.9 Radiomics

The medical record numbers (MRN) for the 65 Mesothelioma patients receiving Pembrolizumab along with their pneumonitis status and scan date will be acquired and forwarded to HIRO. These data will be collected by HIRO and anonymized such that the research team will be provided with the patient scans without any patient-identifying information. HIRO will assign a case-identifying number to each patient in order to label all scans for each patient. Protected patient health information will be stored in password-protected files, and anonymization will comply with the Privacy Rule by removing all 18 private identifiers.

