Trial Period:	Screening Phase		Treatment Cycles [*]								End of Treatment	Post-Treatment		
Treatment Cycle/Title:	Pre-screening (Visit 1)	Main Study Screening (Visit 2)	1	2	3	4	To be repeated beyond 8 cycles ^{**}				Discontinuation (D/C)	Safety Follow-up(+/- 1 week)	Follow Up Visits (+/- 1 week)	Survival Follow-Up(+/- 2 weeks)
							5	6	7	8				
Scheduling Window (Days):		-28 to -1		± 3	± 3	± 3	± 3	± 3	± 3	± 3	At time of D/C	30 days post D/C	Every 8 weeks post D/C	Every 12 weeks
be obtained if biopsy is clinically justified														
Correlative Studies Blood Collection including a) germline DNA collection and b) Flow analysis (See Sections 6.13.6-7)		X ²			X ³									

Laboratory tests for screening or potentially a Second Treatment Course (see Section 8.1.5.2.1) should be performed within 14 days prior to the first dose of treatment. After Cycle 1, pre-dose laboratory procedures can be conducted up to 72 hours prior to dosing.

** Treatment cycle length = 21 days*

*** After cycle 8, as clinically appropriate ECOG performance status, physical exam, and adverse event recording interval may be increased to every other cycle (=every 6 weeks).*

This includes history of asbestos exposure (see Appendix 5—Mesothelioma Program Exposure History Form)

1. If clinically indicated tissue from a biopsy will also be banked using the UCCCC# 9571 banking protocol. The following clinical situations should be considered for obtaining additional tissue for banking purposes and biomarker analysis as outlined below (also see section 6.13.2:.

a) Baseline biopsy e.g. indicated diagnostically, b) Possible tumor flare should be considered for biopsy to assess immune cell infiltration, c) Tumor progression – especially after prior benefit from therapy to rule out pseudoprogression and identify possible mechanisms of resistance using the methodologies described in this section. d) Other clinically appropriate

Trial Period:	Screening Phase		Treatment Cycles *								End of Treatment	Post-Treatment		
Treatment Cycle/Title:	Pre-screening (Visit 1)	Main Study Screening (Visit 2)	1	2	3	4	To be repeated beyond 8 cycles **				Discontinuation (D/C)	Safety Follow-up(+/- 1 week)	Follow Up Visits (+/- 1 week)	Survival Follow-Up(+/- 2 weeks)
							5	6	7	8				
Scheduling Window (Days):		-28 to -1		± 3	± 3	± 3	± 3	± 3	± 3	± 3	At time of D/C	30 days post D/C	Every 8 weeks post D/C	Every 12 weeks

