8.1.5.1 Screening

The screening period is 28 days during which for Part B - PD-L1 testing of tumor tissue, and laboratory, and imaging studies prior to treatment initiation must be completed. See Flow Chart, Section 7.0 for further details.

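### The baseline flow-cytometry blood sample has no drug-free interval of its own, so in some patients it may follow steroids or chemotherapy by only a day or so and give a distorted exploratory baseline

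*Combined protocol and SAP*

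**What the plan says.** **Purpose.** The footnote to section 4.3 covers fresh tissue, "or alternatively/concurrently circulating T-cells) will be assessed for baseline status or treatment effects". Section 9.5 makes the correlative analyses mainly descriptive. It also plans to correlate immune markers, including those measured by flow cytometry, with PD-L1.

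**Sampling.** Section 6.13.8 states: "Blood samples will be obtained at baseline and after cycle 3". It gives no day window and no drug-free interval. In the section 7.1 flow chart, the row "Correlative Studies Blood Collection including a) germline DNA collection and b) Flow analysis" has one pre-dose mark, under Main Study Screening (days -28 to -1), and one on-treatment mark, under cycle 3. Section 8.1.5.1 agrees on the length: "The screening period is 28 days". Table 9 in section 8.1.3.1, however, lists correlative blood among the laboratory tests. The text below that table and the flow-chart footnote ask for screening laboratory tests within 14 days before the first dose.

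**Washouts.** In section 6.1.3, exclusion 3 applies to a patient who "is receiving systemic steroid therapy or any other form of immunosuppressive therapy within 7 days prior to the first dose of trial treatment". Exclusion 5 applies to one who "Has had prior chemotherapy, targeted small molecule therapy, or radiation therapy within 2 weeks prior to study Day 1".

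**Prohibited therapy.** Section 6.7.2 states: "Subjects are prohibited from receiving the following therapies during the Screening and Treatment Phase". Its list includes systemic anti-cancer chemotherapy, radiation (with an exception) and glucocorticoids (with exceptions).

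**The concern.** A washout protects a baseline measurement only if it is complete when the measurement is taken. Here both washouts are tied to dosing, while the sample may be taken up to four weeks earlier. Patients must have progressed on or after pemetrexed and a platinum (section 6.1.1), so recent chemotherapy is plausible.

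If lymphocyte subsets are still recovering from a recent drug at the draw, two things suffer. The baseline value that is to be set against PD-L1 is distorted. In addition, part of any change to cycle 3 may be recovery from the earlier drug rather than an effect of pembrolizumab. With a single arm there is no concurrent group in which to see that recovery.

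**Working it through.** The plan states no figure on this point, so the check is a count of days.

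**Inputs**
- Draw window A: days -28 to -1 (flow chart, section 7.1).
- Draw window B: days -14 to -1 (laboratory rule, section 8.1.3.1 and flow-chart footnote).
- Exclusion 3: days -7 to -1 must be clear, so the last permitted day is -8.
- Exclusion 5: days -14 to -1 must be clear, so the last permitted day is -15.
- Section 6.7.2: prohibition from the start of Screening.

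**Step 1. Exclusions 3 and 5 alone: draw days on which the drug is still permitted**
- Window A, steroids or immunosuppressants: days -28 to -8, 28 - 8 + 1 = 21 of 28.
- Window A, chemotherapy: days -28 to -15, 28 - 15 + 1 = 14 of 28.
- Window B, steroids or immunosuppressants: days -14 to -8, 14 - 8 + 1 = 7 of 14.
- Window B, chemotherapy: 0 of 14.

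**Step 2. Add section 6.7.2.** For chemotherapy, and for glucocorticoids outside the exceptions, the count falls to 0 in both windows.

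**Step 3. Drug-free days guaranteed before the draw.** Take a draw on day -d, the day Screening opens. Section 6.7.2 guarantees nothing before that day, so only the exclusions count. The guaranteed full drug-free days are max(0, 7 - d) for steroids and max(0, 14 - d) for chemotherapy.

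| Draw | Steroids | Chemotherapy |
|---|---|---|
| Day -28 | 0 | 0 |
| Day -14 | 0 | 0 |
| Day -7 | 0 | 7 |
| Day -1 | 6 | 13 |
| Cycle 1 Day 1, pre-dose | 7 | 14 |

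A zero means that the drug may have been given the day before. Examples are chemotherapy on day -15 with a draw on day -14, or steroids on day -8 with a draw on day -7. The shorter 14-day window removes neither case.

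**Step 4. What section 6.7.2 leaves open.** Exclusion 3 covers any immunosuppressant and exclusion 5 covers targeted small molecules, but the 6.7.2 list names neither class. It also allows physiologic corticosteroid doses after consultation, and limited radiation. For these the step 1 counts remain an outer limit, unless another clause applies.

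**Step 5. Effect on results.** The average distortion is the fraction of patients affected times the shift in the marker. The documents give neither, so no figure is offered.

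**The case against.** The strongest reply is that section 6.7.2 already settles the matter. The exclusions set a minimum before dosing, 6.7.2 adds a prohibition from Screening onward, and both can be met together. This stands for concurrent use. A reader might infer from exclusions 3 and 5 that a patient may be sampled while on steroids on 21 of 28 days, or on chemotherapy on 14 of 28. The documents do not support that once 6.7.2 is read with them. What 6.7.2 lacks is an interval before Screening. Pre-screening in the flow chart may lengthen the gap, but no minimum time between the two screening visits is stated.

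Unnamed immunosuppressants may also be covered. Section 6.7 disallows, during the ongoing trial, medications that the exclusion criteria prohibit, and exclusion 8 removes patients with a syndrome requiring such agents. This narrows the gap, but whether the ongoing trial includes Screening is not stated.

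The 28-day window is itself open to dispute because of Table 9. That is fair. The flow chart places the sample in a separate correlative block, so neither window is settled.

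Much of the information needed to identify affected patients is already collected: medications from 28 days before the first dose (sections 6.7.1 and 8.1.1.5.1) and prior cancer treatment (section 8.1.1.6.2). This helps afterwards but does not repair the sample. A steroid stopped on day -29 before a day -28 draw would fall outside the medication record.

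Finally, nothing shows that 7 or 14 days is long enough for recovery. That is correct, and the fix does not claim it.

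**Conclusion.** The concern holds in a limited form. The baseline flow sample has no stated drug-free interval, may follow a stopped drug by a day, and in no charted position carries the full 7 and 14 days that the protocol requires before dosing. Carry-over is possible in some patients, at unknown frequency. It bears on exploratory, descriptive measures only; no primary or secondary endpoint, and no decision on moving from Part A to Part B, depends on it.

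Two stronger readings should be resisted. A reader might infer an inflated rate of false-positive immune effects. Section 9.5 plans no paired test of change in blood cells, and any such rate would need an assumed test, affected fraction and shift. A reader might also infer that on-treatment samples are free of these drugs, so that only the baseline is at fault. They need not be: section 6.2.1.2 directs corticosteroids with a taper of at least 4 weeks for immune-related events, section 6.7.2 permits them for that purpose, and section 6.7.1 allows concurrent radiation.

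The conclusion assumes that the exclusions are followed as written and that a draw may be made on the day Screening opens.

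**What to change.** 1. In section 6.13.8 and the flow chart, move the baseline flow tubes from Main Study Screening to Cycle 1 Day 1, before the first infusion. Every baseline sample then has at least the protocol's own 7 and 14 drug-free days, however the other rules are reconciled. The germline tubes can stay at screening; the footnote's 2 + 2 tubes are consistent with a split.
2. Reconcile exclusions 3 and 5 with the Screening prohibition in section 6.7.2, and the 28-day with the 14-day window for correlative blood.
3. For samples already drawn, use draw dates, recorded medications and prior treatments to flag patients sampled soon after steroids, immunosuppressants or chemotherapy. Section 6.13.6 requires the date and time on the germline tubes; confirm that the same holds for the flow tubes. Also flag cycle 3 samples drawn while on steroids, which item 1 does not address.

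**Cost.** One flow-chart cell and one sentence, with no extra visit, tube or assay; blood count and chemistry are already charted at Cycle 1. The downside is that patients who are screened but never dosed will have no baseline flow sample. They could not contribute to a change from baseline in any case. No eligibility or treatment rule changes under item 1.

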6.2 Trial Treatments

The treatment to be used in this trial is outlined below in *Table 2*

Table 2 Trial Treatment

Drug	Dose/Potency	Dose Frequency	Route of Administration	Regimen/Treatment Period	Use
pembrolizumab	200 mg	Every 21 days	IV infusion	single agent/ongoing for period of treatment benefit	Experimental
The pembrolizumab dosing interval may be increased due to toxicity as described in Section 5.2.1.2.					

6.2.1 Dose Selection/Modification

6.2.1.1 Dose Selection

The rationale for selection of doses to be used in this trial is provided in Section 4.0 – Background and Rationale.

The dose amount required to prepare the pembrolizumab infusion solution will be a flat dose of 200mg. Details on the preparation and administration will be provided by the drug manufacturer on delivery of pembrolizumab.

6.2.1.2 Dose Modification

Pembrolizumab will be withheld for drug-related Grade 4 hematologic toxicities, non-hematological toxicity \geq Grade 3 including laboratory abnormalities, and severe or life-threatening AEs as per Table 3 below.

Table 3: Dose modification guidelines for drug-related adverse events.

Toxicity	Grade	Hold Treatment (Y/N)	Timing for restarting treatment	Dose/Schedule for restarting treatment	Discontinue Subject (after consultation with Drug Manufacturer)
Hematological Toxicity	1, 2	No	N/A	N/A	N/A
	3* *Excluding Grade 3 neutropenia, anemia, and thrombocytopenia	Yes	Toxicity resolves to Grade 0-1 or baseline	May increase the dosing interval by 1 week	Toxicity does not resolve within 12 weeks of last infusion
	4	Yes	Toxicity resolves to Grade 0-1 or baseline	May increase the dosing interval by 1 week	Permanent discontinuation should be considered for any severe or life-threatening event
Non-hematological toxicity	1	No	N/A	N/A	N/A
	2	Consider withholding for persistent symptoms	Toxicity resolves to Grade 0-1 or baseline	Clinical AE resolves within 4 weeks: Same dose and schedule (reference Section 5.6.1.2 for recommendations regarding pneumonitis) Clinical AE does not resolve within 4 weeks: May increase the dosing interval	Toxicity does not resolve within 12 weeks of last infusion

Note:
Exception to be treated similar to grade 1 toxicity

- Grade 2 alopecia
- Grade 2 fatigue

Toxicity	Grade	Hold Treatment (Y/N)	Timing for restarting treatment	Dose/Schedule for restarting treatment	Discontinue Subject (after consultation with Drug Manufacturer)
For additional information regarding Adverse Events with a potential Immune-Etiology reference Section 5.6.1.1.				by 1 week for each occurrence	
	3, 4	Yes	Toxicity resolves to Grade 0-1 or baseline	May increase the dosing interval by 1 week for each occurrence	Toxicity does not resolve within 12 weeks of last infusion Permanent discontinuation should be considered for any severe or life-threatening event

In case toxicity does not resolve to Grade 0-1 within 12 weeks after last infusion, trial treatment should be discontinued after consultation with the PI. With PI agreement, subjects with a laboratory adverse event still at Grade 2 after 12 weeks may continue treatment in the trial only if asymptomatic and controlled. For information on the management of adverse events, see Section 13.3.

Subjects who experience a recurrence of the same severe or life-threatening event at the same grade or greater with re-challenge of pembrolizumab should be discontinued from trial treatment.

Table 3 Dose Modification and Toxicity Management Guidelines for Immune-related AEs Associated with Pembrolizumab

General instructions:				

 1. Corticosteroid taper should be initiated upon AE improving to Grade 1 or less and continue to taper over at least 4 weeks. 2. For situations where pembrolizumab has been withheld, pembrolizumab can be resumed after AE has been reduced to Grade 1 or 0 and corticosteroid has been tapered. Pembrolizumab should be permanently discontinued if AE does not resolve within 12 weeks of last dose or corticosteroids cannot be reduced to ≤ 10 mg prednisone or equivalent per day within 12 weeks. 3. For severe and life-threatening irAEs, IV corticosteroid should be initiated first followed by oral steroid. Other immunosuppressive treatment should be initiated if irAEs cannot be controlled by corticosteroids. 				
Immune-related AEs	Toxicity grade or conditions (CTCAEv4.0)	Action taken to pembrolizumab	irAE management with corticosteroid and/or other therapies	Monitor and follow-up
Pneumonitis	Grade 2	Withhold	
 • Administer corticosteroids (initial dose of 1-2 mg/kg prednisone or equivalent) followed by taper 	
 • Monitor participants for signs and symptoms of pneumonitis • Evaluate participants with suspected pneumonitis with radiographic imaging and initiate corticosteroid treatment • Add prophylactic antibiotics for opportunistic infections
	Grade 3 or 4, or recurrent Grade 2	Permanently discontinue		
Diarrhea / Colitis	Grade 2 or 3	Withhold	
 • Administer corticosteroids (initial dose of 1-2 mg/kg prednisone or equivalent) followed by taper 	
 • Monitor participants for signs and symptoms of enterocolitis (ie, diarrhea, abdominal pain, blood or mucus in stool with or without fever) and of bowel perforation (ie, peritoneal signs and ileus). • Participants with \geq Grade 2 diarrhea suspecting colitis should consider GI consultation and performing endoscopy to rule out colitis. • Participants with diarrhea/colitis should be advised to drink liberal quantities of clear fluids. If sufficient oral fluid intake is not feasible, fluid and electrolytes should be substituted via IV infusion.
	Grade 4	Permanently discontinue		

AST / ALT elevation or Increased bilirubin	Grade 2	Withhold	
 Administer corticosteroids (initial dose of 0.5- 1 mg/kg prednisone or equivalent) followed by taper 	
 Monitor with liver function tests (consider weekly or more frequently until liver enzyme value returned to baseline or is stable)
	Grade 3 or 4	Permanently discontinue	
 Administer corticosteroids (initial dose of 1-2 mg/kg prednisone or equivalent) followed by taper 	
Type 1 diabetes mellitus (T1DM) or Hyperglycemia	Newly onset T1DM or Grade 3 or 4 hyperglycemia associated with evidence of β -cell failure	Withhold	
 Initiate insulin replacement therapy for participants with T1DM Administer anti-hyperglycemic in participants with hyperglycemia 	
 Monitor participants for hyperglycemia or other signs and symptoms of diabetes.
Hypophysitis	Grade 2	Withhold	
 Administer corticosteroids and initiate hormonal replacements as clinically indicated. 	
 Monitor for signs and symptoms of hypophysitis (including hypopituitarism and adrenal insufficiency)
	Grade 3 or 4	Withhold or permanently discontinue ¹		
Hyperthyroidism	Grade 2	Continue	
 Treat with non-selective beta-blockers (eg, propranolol) or thionamides as appropriate 	
 Monitor for signs and symptoms of thyroid disorders.
	Grade 3 or 4	Withhold or permanently discontinue ¹		
Hypothyroidism	Grade 2-4	Continue	
 Initiate thyroid replacement hormones (eg, levothyroxine or liothyronine) per standard of care 	
 Monitor for signs and symptoms of thyroid disorders.
Nephritis and Renal dysfunction	Grade 2	Withhold	
 Administer corticosteroids (prednisone 1-2 mg/kg or equivalent) followed by taper. 	
 Monitor changes of renal function
	Grade 3 or 4	Permanently discontinue		
Myocarditis	Grade 1 or 2	Withhold	
 Based on severity of AE administer corticosteroids 	
 Ensure adequate evaluation to confirm etiology and/or exclude other causes

	Grade 3 or 4	Permanently discontinue		
All other immune-related AEs	Intolerable/ persistent Grade 2	Withhold	
Based on type and severity of AE administer corticosteroids	
Ensure adequate evaluation to confirm etiology and/or exclude other causes
	Grade 3	Withhold or discontinue based on the type of event. Events that require discontinuation include and not limited to: Gullain-Barre Syndrome, encephalitis		
	Grade 4 or recurrent Grade 3	Permanently discontinue		

1. Withhold or permanently discontinue pembrolizumab is at the discretion of the investigator or treating physician.
 
NOTE:
 
For participants with Grade 3 or 4 immune-related endocrinopathy where withhold of pembrolizumab is required, pembrolizumab may be resumed when AE resolves to \leq Grade 2 and is controlled with hormonal replacement therapy or achieved metabolic control (in case of T1DM).
				

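### Section 6.2.1.2 has two tables numbered Table 3 that give different hold, continue or stop instructions for the same immune event and grade, and nothing says which governs

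*Combined protocol and SAP*

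**What the plan says.** All of this sits in Section 6.2.1.2 of the combined protocol and SAP.

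- **Opening sentence.** "Pembrolizumab will be withheld for drug-related Grade 4 hematologic toxicities, non-hematological toxicity" of Grade 3 or above (laboratory abnormalities included), and severe or life-threatening events, with a reference to Table 3.
- **General table.** "Table 3: Dose modification guidelines for drug-related adverse events". Its non-hematological rows are: Grade 1, no hold; Grade 2, "Consider withholding for persistent symptoms"; Grade 3-4, hold, restart once back to Grade 0-1 or baseline, and "Permanent discontinuation should be considered for any severe or life-threatening event".
- **Immune table.** "Table 3 Dose Modification and Toxicity Management Guidelines for Immune-related AEs Associated with Pembrolizumab". It goes event by event. For pneumonitis, the row "Grade 3 or 4, or recurrent Grade 2" carries permanent discontinuation. For hypothyroidism at Grade 2-4 the action is to continue, with the management note "Initiate thyroid replacement hormones (eg, levothyroxine or liothyronine) per standard of care". For myocarditis at Grade 1 or 2 the action is to withhold.
- **References in the general table.** The Grade 2 restart cell reads "Same dose and schedule (reference Section 5.6.1.2 for recommendations regarding pneumonitis", and a note sends immune-etiology events to Section 5.6.1.1. Section 5 ends at 5.2.4.
- **Text below the general table.** Management of adverse events is referred to Section 13.3, which does exist.

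**The concern.** The general table is not limited to non-immune events, and an immune event associated with pembrolizumab is by that attribution drug-related. Both tables therefore apply to it. The opening sentence cannot settle the choice, because the table number it cites belongs to both.

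An investigator can follow one table to the letter and depart from the other. For some events that is the difference between continuing and holding. For pulmonary, hepatic, renal and cardiac immune events it is the difference between a hold with possible restart and permanent discontinuation. This is first a patient-safety matter, and second a source of uneven handling of like events within one trial.

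**Working it through.** No statistical formula applies. The check sets the two tables side by side, one cell for each event and CTCAE grade listed in the immune table, against the general table's non-hematological row for that grade.

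**Cells in the immune table.** Pneumonitis, diarrhea/colitis, AST/ALT or bilirubin, hypophysitis, hyperthyroidism, hypothyroidism, nephritis and other immune events at Grades 2-4: 8 × 3 = 24. Type 1 diabetes or hyperglycemia at Grades 3-4: 2. Myocarditis at Grades 1-4: 4. Total 24 + 2 + 4 = 30.

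| Kind of difference | General table | Immune table | Cells | n |
|---|---|---|---|---|
| Opposite | Hold | Continue | Hypothyroidism G3, G4 | 2 |
| Opposite | No hold | Withhold | Myocarditis G1 | 1 |
| Discretionary vs mandatory stop | Hold, restart allowed, discontinuation considered | Permanently discontinue | G3 and G4 of pneumonitis, AST/ALT or bilirubin, nephritis, myocarditis (8); colitis G4; other immune events G4 | 10 |
| Discretionary vs mandatory hold | Consider withholding | Withhold | G2 pneumonitis, colitis, hepatic, nephritis, hypophysitis, myocarditis | 6 |
| Weaker difference | Consider withholding | Continue; or withhold if intolerable or persistent | G2 hyperthyroidism and hypothyroidism; G2 other immune events | 3 |
| Compatible on hold or stop | Hold, discontinuation considered | Withhold, or withhold or discontinue | Colitis G3; diabetes/hyperglycemia G3, G4; hypophysitis G3, G4; hyperthyroidism G3, G4; other immune events G3 (apart from its named events that require discontinuation) | 8 |

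Sum: 2 + 1 + 10 + 6 + 3 + 8 = 30.

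**Two further differences outside the grid.**

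- *Twelve-week rule.* The text after the general table lets a subject with a laboratory event still at Grade 2 after 12 weeks continue with PI agreement, if asymptomatic and controlled. The immune table's general instructions require permanent discontinuation of an event unresolved at 12 weeks and make no laboratory exception.
- *Restart after Grade 3-4 endocrinopathy.* Grade 0-1 or baseline in the general table; Grade 2 or lower, if controlled, in the immune table's note.

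**Search for a precedence rule.** None was found. Section 6.2.1.2 sends management of adverse events to 13.3. Section 13.3.1 says that its guidance directs when to hold or discontinue, but also that protocol wording is to be followed on dose modification. The reader is returned to 6.2.1.2, where the two tables are not ranked. Section 13.3.1 also contains a third table numbered 3, the list of events of clinical interest.

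**The case against.** **The specific table governs the general one.** The titles invite that reading, and many investigators would adopt it. It is never stated, however, and the general table points the other way: its Grade 2 row names pneumonitis and its note covers events of possible immune etiology, so it treats immune events as within its scope.

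**Most differences are not contradictions.** This stands in part. In the 10 discretionary-versus-mandatory stop cells, a site that discontinues is also within the general table, which asks that discontinuation be considered. The reverse fails: a site that holds and restarts as the general table allows departs from the immune table. Only 3 cells are strictly opposed, and a reader who took the tables to conflict throughout would be wrong.

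**Section 13.3 resolves it.** It is a valid pointer and mostly agrees with the immune table: pneumonitis (13.3.4), colitis (13.3.5), hypothyroidism (13.3.6), hepatic (13.3.8) and renal (13.3.11). Agreement is not complete. For Grade 3 myocarditis, 13.3.13 holds and allows restart, whereas the immune table stops permanently. For Grade 4 hyperthyroidism and hypophysitis, 13.3.6 discontinues, whereas the immune table allows withholding. And 13.3.1 defers back to the protocol.

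**Stronger readings that the documents do not support.**

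- A reader might infer that the opening sentence, which names Grade 4 hematologic toxicity, contradicts the general table's hold at Grade 3. The sentence goes on to cover severe events as per Table 3, and Table 10 in Section 8.2.4 describes Grade 3 as severe. Nor would this be a conflict between the two tables.
- A reader might infer that all 65 planned patients (35 + 30) are affected. That is total enrolment; only those with a listed event at a conflicting grade are.
- A reader might infer that the toxicity summary becomes unreliable. Section 9.5 tabulates toxicity by type and severity, not by dosing action, and no effect on it is shown.

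**Conclusion.** The concern holds as an internal inconsistency in Section 6.2.1.2. Two identically numbered tables overlap in scope without a precedence rule. Three of 30 cells are opposed, 10 differ on whether permanent discontinuation is optional or required, 9 Grade 2 cells differ in strength, and 8 are compatible. The 12-week laboratory rule and the endocrine restart grade also differ.

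This rests on two readings: that an immune event associated with pembrolizumab counts as drug-related, and that the immune table's events fall in the general table's non-hematological rows. The documents give no incidence for these events by grade, so the number of patients who would meet a conflicting instruction cannot be stated. The trial's hypothesis tests and sample size are untouched.

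**What to change.** The sponsor's clinical leads should:

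1. reconcile the two tables cell by cell, starting with the three opposed cells and then the 10 stop cells, and including the 12-week rule and the endocrine restart grade;
2. add one sentence saying which table governs when an event qualifies under both;
3. align the opening sentence of 6.2.1.2 with the result;
4. give the tables distinct numbers, including the one in 13.3.1;
5. replace the references to 5.6.1.1 and 5.6.1.2 with sections that exist, and check 13.3 against the reconciled text.

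Which clinical instruction stands is for them to decide; none is proposed here. The cost is a wording amendment and notification of study staff. There is no statistical cost.
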